#### Secondary objectives

- To determine the prevalence and biomarkers associated with the development of endocrine pancreatic insufficiency following acute pancreatitis (type 3 diabetes mellitus, including new-onset pre-diabetes and/or diabetes mellitus);
- To evaluate changes in gut microbiota according to acute pancreatitis severity;
- To evaluate immunological changes according to acute pancreatitis severity.

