### **C. Expected results, study clinical impact and scientific outputs**

Data on the prevalence and biomarkers of EPI after acute pancreatitis in its different forms of severity and the role of gut dysbiosis and immunologic changes remains unclear. An adequate and timely diagnosis of this clinical condition will allow an early start of therapy with positive impact on clinical course, immunological and gut homeostasis, survival and quality of life. Therefore, a study on the prevalence and biomarkers of EPI in patients with acute pancreatitis, a randomized placebo-controlled trial to determine the timing for start and duration of PERT in EPI and the implications of PERT on gut microbiota and immunological response is urgently needed.

EPI is expected to be a frequent complication of acute pancreatitis, which is likely to increase with acute pancreatitis severity, with significant changes on gut microbiota and immunologic response and an impaired quality of life. Results of this study may have important clinical implications in clinical practice regarding changes in gut microbiota and immunological status, and clinical and nutritional implications of EPI following acute pancreatitis; when to start and for how long PERT should be applied and repercussions of this therapy in clinical course, reverting gut dysbiosis and immunological changes, and improving

quality of life; and the possible benefit of additional unexplored therapies such as gut microbiota modulating therapy including probiotics, prebiotics, symbiotics, fecal microbiota transplantation and targeted immunotherapies. These therapies could have a positive impact in all patients or high-risk group of patients with acute pancreatitis including EPI.

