##### D.3. Study design

This project will take place in 4 distinct phases:

Phase 1: Recruitment of patients with acute pancreatitis and stratification of them according to the severity of acute pancreatitis and development of EPI (12-month follow-up).

All patients admitted to the Gastroenterology Department of Coimbra Hospital and University Centre by the first episode of acute pancreatitis will be included, consecutively, according to the revised Atlanta criteria 2012 and taking into account the inclusion/exclusion criteria and the minimum number of patients needed to obtain statistical power.

Inclusion criteria: Definitive diagnosis of acute pancreatitis, according to revised Atlanta criteria 2012.4

Exclusion criteria: Age <18years; History of allergy, hypersensitivity or contraindication to use of PERT; Prior acute pancreatitis; Other causes that may occur with EPI, including celiac disease, diabetic gastroparesis, chronic pancreatitis, cystic fibrosis, pancreatic neoplasia, ampuloma, somatostatinoma, somatostatin analog therapy, small bowel pathology, inflammatory bowel disease, and rare diseases associated with exocrine pancreatic insufficiency (Zollinger-Ellison syndrome, Shwachman-Diamond syndrome, Johanson-Blizzard syndrome); Prior gastrointestinal or pancreatic surgery or endoscopic/surgical therapy for obesity; medication with orlistat or acarbose; Respiratory pathology (severe chronic obstructive pulmonary disease), hepatic (Child-Pugh C cirrhosis) or biliary (obstructive jaundice) severe pathology; Non-compliance for PERT (when indicated); Uncontrolled thyroid pathology; Refusal/incapacity to give informed consent; and Follow-up period <12months after acute pancreatitis diagnosis.

Sample size calculation: For an estimated prevalence of EPI in the adult population of 25% and a drop-out rate of 10%, it was determined that for a 95% confidence level and 10% sampling error, it will be necessary to include 42 patients in each of the therapeutic arms (PERT vs placebo), making a total of 84 patients.

Diagnosis of EPI and stratification of patients: See Task 1.

Phase 2: Double-blind randomized placebo-controlled trial for patients with EPI after acute pancreatitis for PERT and collection of stool and blood samples before and after

PERT/placebo (6 months post-randomization).

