#### D.4. Statistical analysis

Using of Statistical Package for the Social Sciences (SPSS) version 25.0 (IL, USA). The statistical significance level will be for a p-value < 0.05. The distribution of data normality will be evaluated by Kolmogorov-Smirnov or Shapiro-Wilk tests. Continuous variables will be expressed as mean and standard deviation or median and interquartile range. Categorical variables will be expressed as frequency and percentage. Univariable analysis will be performed using the Kruskal-Wallis test or Anova test (continuous variables) and Qui-squared test test (categorical variables). The Wilcoxon or Friedman test and the t-Student or Anova test will be used to compare paired data. Cox regression multivariable analysis will be used to determine the independent factors associated with exocrine and endocrine pancreatic insufficiencies. Analysis of PERT efficacy will be performed per-Protocol (PP), excluding loss of follow-up and PERT non-compliance. The temporal evaluation of EPI and PERT response will be evaluated through Kaplan-Meier survival curves. The genome sequences will be grouped in OTU according to their similarity. The alpha taxonomic richness and diversity of stool samples will be expressed in observed species and Shannon index. The composition of fecal microbiota will be expressed in rarefaction curves and comparison of the differences in OTU richness with the t-Welch test. Immunological findings will be expressed by radar charts and representative FACS dot-plots. Additional statistical analysis will be defined a posteriori.

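### For comparisons across severity grades, D.4 offers mainly general tests that ignore grade order and, for continuous markers, an ANOVA that assumes equal spread; name an ordered test for EPI and a Welch-type method for markers

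*Combined protocol and SAP*

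**What the plan says.** Section C expects EPI to be a frequent complication, "which is likely to increase with acute pancreatitis severity". The Abstract likewise expects a positive association between severity and EPI. D.3 stratifies the Phase 1 patients by severity. Two of the three secondary objectives in section B concern severity, one for gut microbiota and one for immunology: "To evaluate immunological changes according to acute pancreatitis severity".

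For univariable analysis D.4 lists the "Kruskal-Wallis test or Anova test (continuous variables) and Qui-squared test test (categorical variables". It also plans a two-group Welch t-test for OTU richness and a Cox regression for independent factors associated with exocrine and endocrine insufficiency. The significance rule is "The statistical significance level will be for a p-value < 0.05". Normality is the only assumption it says will be checked. It does not say which test applies to severity or how severity is coded in the Cox model, and it leaves further analyses to be decided afterwards.

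The stated sample size is "it will be necessary to include 42 patients in each of the therapeutic arms (PERT vs placebo), making a total of 84 patients". No size is given for the Phase 1 cohort, in which severity would be compared.

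**The concern.** Two separate issues arise, for different kinds of outcome.

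**Binary outcomes (EPI, endocrine insufficiency).** The plan expects EPI to move in one direction across ordered grades. A chi-squared test gives the same result however the grades are ordered. With three grades it spreads the signal over two degrees of freedom, where a trend test uses one. If the rise is steady, the plan gives up some power to show something it expects.

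**Continuous outcomes (immune and microbiota measures).** Ordinary ANOVA pools the variance over grades. When grades differ both in size and in spread, its error rate departs from 5%. It is too high if the small grades vary most and too low if they vary least. A normality check would not reveal this.

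At stake are the EPI-by-severity result and the two severity-based secondary objectives. The randomised comparison of enzyme replacement with placebo is not affected.

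**Working it through.** **1. The plan's own figure.** D.3 uses a prevalence of 25%, 10% drop-out and precision "for a 95% confidence level and 10% sampling error". Then n = 1.96² × 0.25 × 0.75 / 0.10² = 72.03. Half of this is 36.01, rounded up to 37 per arm; 37 / 0.9 = 41.1, rounded up to 42; and 2 × 42 = 84. The stated total is reproduced. It is a precision calculation for one proportion and contains no input about severity.

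**2. Assumptions needed.** The documents do not give the number of grades, their shares, EPI by grade or marker SDs. I assume three grades scored 0, 1, 2. Cohort sizes are 84 (the stated total), 150 (intermediate) and 336 (84 / 0.25, the cohort needed to yield 84 EPI cases). Tests are two-sided at 5%.

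**3. EPI by grade.** With grade sizes n_j, rates p_j, overall rate p̄, scores x_j and weighted mean score x̄, the noncentralities are:

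- unordered test, 2 df, critical value 5.99: λ = Σ n_j (p_j − p̄)² / [p̄(1 − p̄)]
- trend test, 1 df, critical value 3.84: λ_T = [Σ n_j p_j (x_j − x̄)]² / [p̄(1 − p̄) Σ n_j (x_j − x̄)²]

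Example: grades of 218/84/34 (65/25/10% of 336) and EPI of 20/30/40%. Then p̄ = (43.6 + 25.2 + 13.6) / 336 = 0.245, and λ = (0.446 + 0.252 + 0.814) / 0.185 = 8.17. The rise is exactly linear, so λ_T is also 8.17. Power is 73% unordered and 82% for trend (72% and 80% by simulation).

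| Grade sizes | EPI by grade | Unordered | Trend |
|---|---|---|---|
| 50/21/13 | 18/30/42% | 38.0% | 47.7% |
| 90/38/22 | 18/30/42% | 60.7% | 70.9% |
| 202/84/50 | 18/30/42% | 93.2% | 96.5% |
| 202/84/50 | 20/28/40% | 77.6% | 85.0% |
| 50/21/13 | 22/22/45% | 32.7% | 30.4% |
| 202/84/50 | 22/22/45% | 88.0% | 80.9% |
| 218/84/34 | 20/20/40% | 66.3% | 54.2% |
| 218/84/34 | 22/22/45% | 76.0% | 63.1% |

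Under a steady rise the trend test gains 3.3 to 10.2 points. If only the top grade differs it loses 2.3 to 12.9 points. In intermediate shapes the two are about equal: at 218/84/34, both have about 93% for 20/25/50% and 95% for 20/40/40%.

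With equal rates of 25% in every grade, the chi-squared test rejected in 4.8 to 5.2% of simulated studies, whatever the grade sizes.

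**4. Continuous markers by grade.** Simulated rejection rates at nominal 5%, normal data, no true difference:

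| Grade sizes | SD ratio | ANOVA | Kruskal-Wallis | Welch ANOVA |
|---|---|---|---|---|
| 50/21/13 | 1:1.5:2 | 14% | 10% | 5% |
| 218/84/34 | 1:1.5:2 | 17–18% | 10% | 4–5% |
| 50/21/13 | 2:1.5:1 | 1% | 2% | 4% |
| 28/28/28 | 1:1.5:2 | 6% | 6% | 6% |

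A milder SD ratio of 1:1.25:1.5 at 218/84/34 gives ANOVA 12% and Welch 5%. A more uneven 59/17/8 split with SDs 1:1.5:2 gives ANOVA 19% and Welch 5%.

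Cost of Welch when spread is equal: for a marker rising 0.2 SD per grade at 218/84/34, power is 57% against 58% for ANOVA.

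**The case against.** The strongest reply is that D.4 never assigns these tests to severity. The quoted sentence is a general list, and the Cox regression, which is the planned analysis of independent factors for EPI, could carry severity as an ordered term. Unordered tests are also valid for exploratory secondary objectives, and skewed cytokines would probably go to Kruskal-Wallis rather than ANOVA.

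Much of this stands. That the list applies to severity is an inference, though apart from the Welch t-test and the Cox model nothing else in D.4 compares independent groups. The Cox model could use the order, but D.4 does not say so, and it covers only the two insufficiencies, not microbiota or immunology. Kruskal-Wallis is not an equal-variance test in the ANOVA sense, but at about 10% it is also affected by unequal spread.

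Four stronger readings are tempting and not supported:

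- A reader might infer that the chi-squared test for EPI has an inflated error rate. It has no equal-variance assumption and kept its 5% level.
- A reader might infer that the unordered test gives up power for nothing in return. It protects against non-linear patterns. The Abstract links EPI to necrosis as well as severity, so a step at the top grade is plausible.
- A reader might infer that ANOVA p-values here will be too small. The direction depends on which grade varies most, and no SDs are given.
- A reader might take Jonckheere-Terpstra as the cure for unequal spread. It rejected in about 8% of null studies at SDs 1:1.5:2.

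**Conclusion.** The point holds as a gap in specification, with a better method available at little cost. The case is firmer for continuous markers. Welch ANOVA stayed close to 5% whichever way spread varied and cost about one point of power when spread was equal. Ordinary ANOVA ranged from about 1% to about 14 to 18% when the extreme grades' SDs differed twofold, under 60/25/15% and 65/25/10% splits. With equal grade sizes the problem almost disappears.

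For EPI the choice is one of efficiency, not validity: roughly 3 to 10 points gained under a steady rise, against roughly 2 to 13 lost if only the top grade differs. The plan's stated expectation favours using the order, but an expected increase does not imply equal steps. For endocrine insufficiency the documents state no direction by severity, so the case there is by extension.

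Every size quoted rests on assumed grades, shares, rates and SDs. What does not depend on them is that D.4 names neither the severity test nor the coding of severity, and leaves room to choose both after the data are seen.

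**What to change.** Add to D.4:

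1. For continuous immune and microbiota measures by severity, use Welch ANOVA in place of ordinary ANOVA, or a linear contrast across grades with unequal-variance standard errors. State which one is used.
2. For EPI and endocrine insufficiency by severity, name one primary test that uses the order: either Cochran-Armitage, or severity as an ordered term in the planned Cox model. Give the grades and their scores. Keep the unordered test as a secondary check for non-linearity, and state that the ordered test decides.

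This costs a few sentences of SAP text and needs no extra patients, visits or samples. The price of item 2 is lower power if the excess is confined to the top grade. The secondary check can show such a pattern but does not restore the primary test's power. If the investigators expect a step rather than a gradient, they should write that contrast in before seeing the data.

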**Methods:** Prospective longitudinal study of total of patients consecutively admitted to the gastroenterology Department of Coimbra Hospital and University Centre with acute pancreatitis diagnosis and double-blind randomized placebo-controlled clinical trial of PERT in patients developing EPI after acute pancreatitis. This study will be conducted in 4 Phases: Phase 1 - Recruitment of patients with acute pancreatitis and stratification of them according to the severity of acute pancreatitis and development of EPI (12-month follow-up), diagnosed by fecal elastase-1, C-labeled mixed triglyceride breath test assessing exocrine pancreatic function and comparison of them with 72-hour fecal fat quantification, as gold standard; Phase 2 – Double-blind randomized placebo-controlled trial in patients with EPI after acute pancreatitis for PERT with assessment of efficacy and safety of this therapy at 1 and 6 months post-randomization; Phase 3 - Evaluation of richness, diversity and uniformity of gut microbiota by DNA sequencing using the hypervariable region of the 16S ribosomal RNA gene as a taxonomic identification marker and assessment of quality of life using SF-36 and QLC-C30-V.3 scales (validated versions for the Portuguese population) in EPI patients after acute pancreatitis, and the impact of PERT on clinical course, gut dysbiosis and quality of life of patients (at the diagnosis of acute pancreatitis, EPI and after PERT); and Phase 4 – Analysis of immunological changes through the study of cell populations by flow cytometry (CD4+, CD8+, B-cell, T-cell, natural killer cells, cells ratio) and cytokines, chemokines and growth factors by xMAP/Luminex, at the diagnosis of acute pancreatitis, EPI and after PERT.

**Expected results, impact and scientific outputs:** Data on the prevalence of EPI after acute pancreatitis in its different forms of severity and the role of gut dysbiosis and immunologic changes remains unclear. It's expected that an adequate and timely diagnosis of this clinical condition will allow an early start of therapy with positive impact on clinical course, immunologic and gut homeostasis, survival and quality of life. With this study we expect to obtain a prevalence of EPI at admission of 25-62%, which should decrease during

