followup. Alcoholic etiology, severity of acute pancreatitis and the presence of pancreatic necrosis should be positively associated with the presence of EPI after acute pancreatitis. The prevalence of endocrine pancreatic insufficiency (pre-diabetes or diabetes mellitus) should be up to 40%. Nutritional deficits (single or multiple), breath test assessing exocrine pancreatic function and fecal elastase-1 are also expected to be positively associated with the development of EPI. It's expected that patients with acute pancreatitis developing EPI will have significant changes on gut microbiota and immunologic response, and PERT and/or gut microbiota modulating therapy, including prebiotics, probiotics, symbiotics and fecal microbiota transplantation, and probably targeted immunotherapies may have a beneficial impact on all patients or groups at risk, such as EPI, severe or necrotizing acute pancreatitis by reverting gut and immunologic dysbiosis, and improving quality of life.

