Randomization of patients with EPI following acute pancreatitis for PERT vs placebo. The efficacy, safety and compliance of PERT will be evaluated at 1 (for adjusting PERT dose) and 6 months after PERT start.

Phase 3: Analysis of gut microbiota and assessment of quality of life, and the impact of PERT on clinical and nutritional course, gut dysbiosis and patients' quality of life (at the diagnosis of acute pancreatitis, EPI and after PERT). Evaluation of richness, diversity and uniformity of gut microbiota by DNA sequencing

using the hypervariable region of the 16S rRNA gene. Assessment of quality of life using validated Portuguese versions of SF-36 and QLC-C30-V.3 Assess of PERT impact on clinical and nutritional course, gut dysbiosis and patients' quality of life.

Phase 4: Analysis of immunological changes and the impact of PERT on clinical and nutritional course and immunological status (at the diagnosis of acute pancreatitis, EPI and after PERT). Evaluation of immunological changes through the study of cell populations by flow cytometry (CD4+, CD8+, B-cell, T-cell, natural killer cells, cells ratio) and cytokines, chemokines and growth factors by xMAP/Luminex. Assess PERT impact on clinical and nutritional course and immunological changes.

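### Cox regression is the only multivariable model planned for EPI factors, although 25-62% of patients are expected to have EPI at admission and so have no time at risk

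*Combined protocol and SAP*

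**What the plan says.** Section D.4 gives one multivariable method for risk factors: "Cox regression multivariable analysis will be used to determine the independent factors associated with exocrine and endocrine pancreatic insufficiencies". For the course over time it says: "The temporal evaluation of EPI and PERT response will be evaluated through Kaplan-Meier survival curves". It states no time origin, no event, and no rule for EPI that is present at entry or that resolves. Further analyses are left to be defined afterwards.

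The abstract sets the expectation: "With this study we expect to obtain a prevalence of EPI at admission of 25-62%, which should decrease during" follow-up. It also expects that "the presence of pancreatic necrosis should be positively associated with the presence of EPI after acute pancreatitis". Among the exclusion criteria in D.3 is "Follow-up period <12months after acute pancreatitis diagnosis".

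Section B makes the prevalence, duration and biomarkers of EPI the first primary objective. For diagnosis, D.3 says "Diagnosis of EPI and stratification of patients: See Task 1", and that task is not in the supplied text.

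**The concern.** Cox regression models the time to an event among people who have not yet had it. Here a quarter to over half of the patients are expected to have the condition when the clock starts, some are expected to lose it, and everyone analysed is followed for 12 months. There is little censoring for Cox to handle, and the patients who supply most of the information have no time at risk.

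The analyst would have to choose between dropping these patients and tying them at time zero. The two routes answer different questions, and D.4 does not choose between them. The choice could therefore be made after the data are seen, for an analysis that serves the first primary objective. The undefined Kaplan-Meier event raises the same difficulty for duration.

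**Working it through.** **The plan's own figure.** D.3 concludes that "it will be necessary to include 42 patients in each of the therapeutic arms (PERT vs placebo), making a total of 84 patients". Its inputs are 25% prevalence, 10% sampling error, 95% confidence and 10% drop-out.
- 1.96² × 0.25 × 0.75 / 0.10² = 72.03, rounded up to 73.
- Half per arm is 36.5, rounded up to 37. Then 37 / 0.9 = 41.1, rounded up to 42 per arm, or 84 in total.

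The figure reproduces. It is a precision calculation for one proportion and sets no event count for a Cox model.

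**Share of first-EPI events at time zero.** Let p be the prevalence at admission (25% and 62%, from the abstract) and r the later onset among patients free of EPI at admission (assumed 5%, 10%, 20%). The share is p / [p + (1 − p)r].

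| p | r | Later events per 100 patients, 100(1 − p)r | Share at time zero |
|---|---|---|---|
| 25% | 5% | 3.75 | 0.25 / 0.2875 = 87.0% |
| 25% | 10% | 7.5 | 0.25 / 0.325 = 76.9% |
| 25% | 20% | 15 | 0.25 / 0.40 = 62.5% |
| 62% | 5% | 1.9 | 0.62 / 0.639 = 97.0% |
| 62% | 10% | 3.8 | 0.62 / 0.658 = 94.2% |
| 62% | 20% | 7.6 | 0.62 / 0.696 = 89.1% |

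**Route 1: drop the admission cases.** Only the later events in the third column remain, and the question becomes one of later onset. A simulation illustrates this. It assumed 84 patients, 30% exposed, 35% EPI at entry in the unexposed, 15% later onset, and a factor with odds ratio 3 for EPI at entry, better persistence and no effect on later onset. Logistic regression of entry status gave a median odds ratio of 3.04. Cox among those free of EPI at entry gave a hazard ratio of 0.98 and rejected in 3% of runs. Cox is right about onset here, but it says nothing about presence.

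**Route 2: tie them at time zero.** Take the limiting case in which all events are at one time and the factor is binary, with d₁ of n₁ and d₀ of n₀ affected. The Breslow estimate is log[(d₁/n₁)/(d₀/n₀)], the log risk ratio, so Cox has become a regression of status. Its model-based variance is 1/d₁ + 1/d₀. The correct variance is 1/d₁ − 1/n₁ + 1/d₀ − 1/n₀. Under the null the standard error is too large by 1/√(1 − p):
- p = 25%: 1/√0.75 = 1.15
- p = 62%: 1/√0.38 = 1.62

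This is conservative. At 25%, with an inferred cohort of 84 / 0.25 = 336, half exposed and an odds ratio of 2.5, simulated power was 90.2% for model-based Cox, 94.5% with robust variance and 94.7% for logistic regression.

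**Kaplan-Meier.** If the event is first EPI, one minus the curve can only rise. Assume 5% later onset and 30% or 60% resolution by 12 months.
- From 25%: true 12-month prevalence is 0.25 × 0.7 + 0.0375 = 21% or 0.25 × 0.4 + 0.0375 = 14%. The curve reads 0.25 + 0.0375 = 29% in both cases.
- From 62%: true prevalence is 0.62 × 0.7 + 0.019 = 45% or 0.62 × 0.4 + 0.019 = 27%. The curve reads 0.62 + 0.019 = 64% in both cases.

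If the event is resolution, timed from EPI diagnosis, the curve describes duration directly.

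**The case against.** The strongest reply is that the plan also asks about onset. The first primary objective and Phase 1 in D.3 both speak of EPI developing, and time to onset is a proper use of Cox. EPI at admission appears only in the abstract's expected results; section C does not repeat it. This stands in part: Cox for later-onset EPI should stay and be reported beside the status model. It does not give patients who already have EPI any time at risk. If the unseen task places the first EPI assessment later than admission, the tied block moves to that visit and the Breslow algebra is the same.

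A reader might infer that the planned Kaplan-Meier curve cannot describe duration. The documents do not support that. D.4 never says the event is first EPI, and resolution is a natural reading given the duration objective.

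A reader might also infer that Cox would produce false positives. It would not: the tied analysis is conservative, only slightly so at 25%, and robust variance removes the excess.

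Finally, D.4 already reports categorical variables as frequencies and percentages, so prevalence by visit may be intended. What is missing is the explicit statement and the interval.

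**Conclusion.** The point holds for factors associated with the presence of EPI. On the plan's own expectation of 25-62% at admission, Cox either discards those cases or becomes a regression of status. With later onset of 5-20%, 63-87% (at 25%) or 89-97% (at 62%) of first-EPI events fall at time zero. The later-onset rates are assumptions, as the documents give none; the lack of time at risk does not depend on them.

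The Kaplan-Meier part is conditional: the event must be defined, and only the first-EPI reading fails. New-onset endocrine insufficiency is not affected. Nor does the finding show that the plan lacks EPI criteria or visit times, which may be in the task that was not supplied. The sample size does not change. The correction is worth making before analysis because a primary objective depends on it.

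**What to change.** Reword D.4 as follows.
- **Prevalence:** report EPI prevalence with 95% confidence intervals at admission and at each EPI assessment to 12 months.
- **Factors associated with presence:** replace Cox with multivariable logistic regression of EPI status at admission (or Poisson with robust variance if a risk ratio is wanted). Add status at 12 months as a supportive analysis. D.3 provides for "Randomization of patients with EPI following acute pancreatitis for PERT vs placebo", so prespecify how randomised arm is accounted for after randomisation. Do not use a covariate with a not-randomised level: that level means EPI-free, so it conditions on the outcome.
- **Onset:** keep Cox for later-onset EPI among patients free of EPI at admission, reported alongside the status model, and for new-onset endocrine insufficiency.
- **Duration:** state that the Kaplan-Meier event is documented resolution, timed from EPI diagnosis, among EPI patients and by arm.

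Take EPI criteria and visit times from the task cited in D.3 if they are there.

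The cost is analysis wording, with the same data and standard methods. The status models ignore the timing of onset, and admission status is cross-sectional. The 12-month model has fewer events. For illustration, if all 84 EPI patients have it at admission and admission prevalence is 40%, the inferred cohort is 84 / 0.40 = 210. At the 26.1% that the literature review reports for 12-36 months, 210 × 0.261 gives about 55 events. At an assumed 10 events per covariate, that supports 5 covariates rather than 8, and fewer still if PERT patients are left out to handle treatment.

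### PERT efficacy is to be analysed per-protocol only, so the randomised comparison is not preserved and the estimate can be biased in either direction

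*Combined protocol and SAP*

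**What the plan says.** Section B makes the efficacy of PERT a primary objective, and D.3 (Phase 2) tests it by randomisation: "Randomization of patients with EPI following acute pancreatitis for PERT vs placebo". D.4 then sets the analysis population: "Analysis of PERT efficacy will be performed per-Protocol (PP), excluding loss of follow-up and PERT non-compliance". It names no other population, no missing-data method and no sensitivity analysis, and it ends with "Additional statistical analysis will be defined a posteriori".

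Compliance is observed during treatment, not at entry: "The efficacy, safety and compliance of PERT will be evaluated at 1 (for adjusting PERT dose) and 6 months after PERT start". Even so, the exclusion criteria in D.3 include "Non-compliance for PERT (when indicated" and also "Follow-up period <12months after acute pancreatitis diagnosis". The only attrition figure in the document is the 10% drop-out allowance in the sample size paragraph of D.3, which leads to 42 patients per arm.

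**The concern.** Randomisation makes the arms comparable when patients are allocated. Removing patients for what happens later can undo that, because leaving the study or stopping treatment may be related both to the arm and to how the patient is doing. Three features of this plan make the risk concrete.

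- The excluded event is non-compliance with PERT. Placebo is not mentioned and no threshold is given. The rule could filter the active arm only, or both arms; the text does not say which.
- Patients may stop because they do badly or because they recover. The abstract says "With this study we expect to obtain a prevalence of EPI at admission of 25-62%, which should decrease during" follow-up, so recovery is a realistic reason to stop, and it pushes the bias the other way.
- The 12-month rule can discard an observed result. A patient randomised *m* months after diagnosis reaches the 6-month assessment at about *m* + 6 months, which is before month 12 whenever *m* < 6.

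The analysis could therefore show a benefit of PERT that does not exist, or hide one that does. No other pre-specified efficacy analysis would reveal it.

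**Working it through.** **1. The plan's own figure.** Inputs from D.3: prevalence 25%, sampling error 10%, confidence 95%, drop-out 10%.

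- n = 1.96² × 0.25 × 0.75 / 0.10² = 72.03, rounded up to 73.
- Split over two arms: 36.5, rounded up to 37.
- Allowing for drop-out: 37 / 0.90 = 41.1, rounded up to 42 per arm, 84 in total.

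The figure reproduces, but as a precision calculation for a prevalence. It contains no treatment effect, no power and no separate allowance for non-compliance. At 10% exclusion, about 38 of 42 per arm remain (42 × 0.90 = 37.8).

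**2. Bias when the outcome is continuous.** The model is assumed: outcome N(0,1) with higher values better, no true effect, 42 per arm, two-sided t test at 0.05. In each arm, latent compliance has correlation ρ with outcome and the lowest fraction f is excluded. The mean outcome of those kept is ρ·φ(z_f)/(1−f), so

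bias = ρ₁·φ(z_f₁)/(1−f₁) − ρ₀·φ(z_f₀)/(1−f₀), with arm 1 = PERT.

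φ(z_f)/(1−f) is 0.195, 0.350 and 0.497 for f = 10%, 20% and 30%. Each simulated scenario used 40,000 trials. A positive sign favours PERT.

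| Excluded, PERT / placebo | ρ | Formula (SD) | Simulated (SD) | Type I error |
|---|---|---|---|---|
| 10% / 0 | 0.5 | 0.5 × 0.195 = +0.10 | +0.098 | 7.0% |
| 10% / 10% | +0.5 / −0.5 | 0.0975 + 0.0975 = +0.195 | +0.195 | 13.9% |
| 10% / 10% | −0.5 / +0.5 | −0.195 | −0.196 | 14.0% |
| 20% / 0 | 0.5 | 0.5 × 0.350 = +0.175 | +0.175 | 11.8% |
| 20% / 0 | −0.5 | −0.175 | −0.174 | 11.5% |
| 30% / 10% | 0.5 | 0.248 − 0.097 = +0.15 | +0.149 | 9.5% |
| 10% / 20% | 0.5 | 0.097 − 0.175 = −0.08 | −0.077 | 6.4% |
| 20% / 20% | 0.5 | 0 | +0.001 | 4.9% |

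At 10% in the PERT arm only with ρ = 0.3, the bias is 0.3 × 0.195 = +0.06 SD and the type I error about 6%. At 10% in both arms for the same reason, the bias is 0.00 SD and the type I error 5%. For PERT-only exclusion of 10-30% at |ρ| of 0.3-0.8, the range is −0.40 to +0.40 SD with type I error 6-41%. The extremes need 30% exclusion at 0.8 (0.8 × 0.497 = 0.40).

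**3. When a true effect exists.** The plan states none, so take 0.62 SD, which gives 80% power at 42 per arm. Excluding 20% of the PERT arm because they recovered (ρ = −0.5) cuts the estimate to 0.44 SD and power to 49%. Excluding 20% from both arms for the same reason leaves 0.62 SD and 75% power.

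**4. Check with a binary outcome.** Assume 50% response in both arms, 21/42 in each. Dropping four non-responders from PERT and four responders from placebo gives 21/38 = 55.3% against 17/38 = 44.7%, a false difference of 10.5 points. Swapping the arms reverses the sign. In a separate simulation of 200,000 trials with opposite mechanisms at 10%, type I error was 16.5%, against 6.3% for all randomised patients with the same pooled z test.

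**5. What an all-randomised analysis recovers.** With complete outcomes it gives 0.00 SD and 5%. Suppose 20% of the PERT arm stop treatment (ρ = 0.5) and half of them have missing outcomes that are ignored: +0.08 SD and 6% remain.

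**The case against.** **Missing data.** If the 10% drop-outs have no 6-month outcome, an analysis of all randomised patients with observed data gives the same estimate as per-protocol. The bias at 10% is then a missing-data problem, which a change of analysis set alone does not solve. This stands, and it is why the fix needs outcome collection and a missing-data method. The direct gain from the wider set comes from non-compliers whose outcomes are observed, and the plan gives no rate for them.

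**Assumptions.** The document supplied states no PERT efficacy endpoint. The outcome model, the correlations, all rates above 10% and the 0.62 SD effect are assumed. The figures show that bias is possible in both directions; they do not predict its size.

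**Blinding.** D.1 says the patient will not know the treatment, which makes exclusion driven by knowledge of the arm less likely. It does not prevent exclusion driven by tolerability or response. D.1 also does not list whoever judges compliance among those blinded.

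**Other analyses.** D.4 attaches no exclusion to the Kaplan-Meier and microbiota analyses, and D.3 refers to a Task 1 that is not in the supplied text. But Kaplan-Meier is a method, not a second population, and D.4 is the statistical section. It states a per-protocol rule for efficacy.

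**Scope of the exclusion criteria.** Both criteria sit under Phase 1 and may have been meant for the cohort. The text does not limit them to it, so their scope has to be stated.

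**Conclusion.** The concern holds and should be fixed before any comparison by arm. The only pre-specified efficacy analysis for a randomised primary objective removes patients for post-randomisation events, and no all-randomised analysis is planned beside it. At the plan's own 10% attrition, the illustrated effect runs from nil (same reason in both arms), through +0.06 to +0.10 SD with type I error 6-7% (PERT arm only), to 0.20 SD in either direction with type I error 14% (opposite reasons). Larger figures need higher assumed exclusion rates or stronger correlations. The seriousness comes from the structure of the plan more than from any one figure: an analysis added after the data are seen would be post hoc.

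**What to change.** Replace the per-protocol sentence in D.4 with wording such as:

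> The primary PERT efficacy analysis includes all randomised patients in the arm assigned, regardless of compliance. The 6-month assessment is sought from everyone, including those who stop study treatment. Missing outcomes are handled by a method suited to each outcome (for example multiple imputation or a mixed model), with its assumption stated and a sensitivity analysis for outcome-dependent loss. Kaplan-Meier analysis of PERT response counts all randomised patients from randomisation and does not censor at stopping study treatment. A per-protocol sensitivity analysis uses one compliance definition applied identically to PERT and placebo, and exclusions are reported by arm with reasons.

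In D.3, state that PERT non-compliance and follow-up shorter than 12 months are not grounds for excluding randomised patients from the trial comparison. The Kaplan-Meier sentence corrects no stated rule; it fixes a point on which the plan is silent.

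The cost is SAP wording, plus follow-up to an already planned visit for patients who stop treatment. The estimate may be diluted by non-compliers, and any outcomes still missing will need an assumption that cannot be tested.
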